Transcranial Doppler (TCD) is a technique that explores cerebral blood flow velocities¹¹. In patients with TBI, this technique can reveal low diastolic blood flow velocity (FVd) and high pulsatility index (PI) values induced by high vascular bed resistance. TCD has been used on admission to improve cerebral hemodynamics in patients with severe TBI¹². Surprisingly, little studies conducted in patients with mild and moderate TBI.

In a study by **Bouzat et al., 2011**, including patients with normal or mild brain lesions on initial CT scan, they found a correlation between TCD measurements on admission and early neurologic status. The thresholds of 1.25 and 25 cm/s for PI and FVd accurately predicted neurologic worsening with 90% sensitivity and 91% specificity².

Also, cohort study by **Bouzat et al., 2016**, found that TCD measurement threshold had high negative predictive value (NPV) to predict neurological worsening despite low incidence while the positive predictive value (PPV) of TCD to predict SND was low⁵.

As it was a limitation in previous study, we will use wider range of threshold rather than strict cutoff threshold.

Aim of the work

The aim of our research will be to study the utility of Transcranial Doppler Pulsatility Index in mild and moderate traumatic brain injury for early prediction of neurological deterioration.

Patients and methods

This prospective study will be carried out in Tanta Emergency Hospitals for one year starting after approval from Ethics Committee on 105 patients with mild to moderate traumatic brain injury (TBI).

After approval from Institutional Ethics Committee an informed consent will be obtained from each participant. All data of patients will be confidential with secret codes and private file for each patient. All given data will be used for the current medical research only.

Any unexpected risks appeared during the course of the research will be cleared to participants and the ethical committee on time. Each participant will receive an explanation to the purpose of the study and have secret code number to ensure privacy to participants and confidentiality of data.

Inclusion criteria:

Any adult patient aged (25_60) years presented with mild to moderate TBI (GCS 9 – 15) admitted to Emergency Hospitals within 12 hours following the trauma.

Exclusion criteria:

- Patient underwent head surgical procedure before admission.
- History of previous intracranial lesion.
- History of treatment with anticoagulant and /or antiplatelet.
- TBI more than 12 hours following trauma.
- Mechanically ventilated patients with sedation on admission.
- Systolic arterial blood pressure less than 90 mmHg and /or arterial pulse oximetry less than 90%.

- Evidence of severe brain lesions on initial CT scan (*i.e.*, *Traumatic Coma Data Bank* TCDB classification III-VI)¹⁴
- Any craniotemporal lesion impeding satisfactory TCD examination

Each patient will be undergoing:

- History (from patient and attendance).
- General and neurological examination.
- Monitoring (noninvasive blood pressure, Electrocardiography, oxygen saturation (SaO₂))
- Laboratory investigation(Hb concentration, serum Na and K concentration and arterial blood gases (ABG))
- Equipment:
Doppler Ultrasound machine (SonoScape[®], SSI-6000, China).
Ultrasound probe 2 - 5 MHz.
Sterile gloves, towels and gel.
- Method:
Both middle cerebral arteries will be insonated through the transtemporal window at a depth of 50 to 60 mm, and tracings will be recorded for at least 10 cardiac cycles in patients showing stable conditions, *i.e.*, no agitation or pain, no cardiorespiratory distress. The clinoid process of the sphenoid bone and the brain stem will be initially identified. Color-coded sonography will enable identification of the circle of Willis. The middle cerebral artery (MCA) will be identified and manual angle correction then will be applied to measure blood flow velocity in each MCA (in centimeter per second). Tracings will be stable over a 30-s recording period. Time-averaged mean blood flow velocity (FVm), systolic blood

flow velocity (FVs), diastolic blood flow velocity (FVd) (in centimeter per second) and the PI [(FVs – FVd)/FVm] will be calculated².

All patients will have TCD measurements immediately on admission and will be classified into groups according to PI value and the outcome.

Measurements:

All data will be recorded by a physician not included in the research.

- Age, sex, Glasgow coma scale¹³, comorbidities and the cause of trauma.
- The length of stay in the hospital and ICU.
- The heart rate, blood pressure, Sao_2 and $Paco_2$ every 12 hr in first 48 hr then every day till 7th day.
- Head CT classification by (TCDB classification) ¹⁴ on admission.
- Pulsatility index (PI) will be measured on admission then every 12hr following admission for 1st 48 hour after that every day till 7th day.
- Secondary neurological deterioration (SND)¹⁵ (one of the two objective criteria: (1) a decrease in GCS of greater than 2 points from the initial GCS in the absence of pharmacologic sedation (2) a deterioration in neurologic status sufficient to warrant intervention, *i.e.*, mechanical ventilation, sedation, osmotherapy, or neurosurgical intervention) after 48hr till the 7th day.
- Extended Glasgow Outcome Scale (GOSE) ¹³after one month.

Primary outcome:

SND at 7th day post traumatic.

Secondary outcomes:

Length of stay in ICU and GOSE after one month.

Sample Size Calculation:

Using MedCalc program version 18.2.1 (MedCalc Software, Ostend, Belgium), the sample size is calculated as 105 patients. The sample size calculated by the following criteria:

- 5% confidence limit.
- 80% power of the study.
- According to a previous study ⁽²⁾, area under the curve (AUC) for PI to predict the outcome (SND) was 0.86 and 6% of patients developed SND within the first week after trauma.
- 16 cases were added to overcome drop out.

Results

All results will be tabulated and statistically analyzed.

Discussion

The results will be discussed later.

References

- 3) **Compagnone C, d'Avella D, Servadei F, et al.** Patients with moderate head injury: a prospective multicenter study of 315 patients. *Neurosurgery.* 2009 Apr 1;64(4):690-7.

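### Is a sample sized on the AUC too small for the range of thresholds that the protocol says it will use?

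*Protocol*

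**What the plan says.** The last paragraph before Aim of the work in the Protocol, referring to a limitation of the previous study, states: "we will use wider range of threshold rather than strict cutoff threshold". It lists no thresholds and names no accuracy measure. Under Method, patients "will be classified into groups according to PI value and the outcome", again without cut-points.

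Sample Size Calculation uses different terms. It cites an earlier study in which "area under the curve (AUC) for PI to predict the outcome (SND) was 0.86". The assumed event rate comes from the same source: "6% of patients developed SND within the first week after trauma". The section sets a 5% level and "80% power of the study", adds that "16 cases were added to overcome drop out", and concludes that "the sample size is calculated as 105 patients". The AUC against which 0.86 is compared is not given. No target is set for sensitivity or specificity at any threshold.

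The aim is to study the utility of the pulsatility index (PI) for early prediction, and the primary outcome is SND at day 7. Measurements counts SND "after 48hr till the 7th day".

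**The concern.** The range of thresholds is presented as this study's improvement on earlier work, yet the sample size is built on the AUC alone. An AUC that differs from chance does not tell a reader how many deteriorating patients a given PI value would miss. That is a question of sensitivity, which here is a count out of five or six people and moves in steps of 17 to 20 points.

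Two thresholds of very different worth could look alike. As an illustration with chosen values, suppose one threshold truly misses 40% of SND cases and another 10%. With five cases, the first would show at most one miss in 34% of studies and the second in 92% (23% and 89% with six cases). Negative predictive value would hardly separate them. At 6% SND and an assumed 80% specificity it is 96.9% for 60% sensitivity and 99.2% for 90%, while flagging nobody already gives 94%. A cut-off taken from such data into practice could be a poor one. Dividing the same few cases among PI groups would thin them further.

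**Working it through.** **Inputs.** From Sample Size Calculation: 105 patients in all, 16 of them for drop-out, 5% level (two-sided assumed), 80% power, AUC 0.86, SND 6%. From the background: 90% sensitivity and 91% specificity in an earlier study. The comparison AUC is not stated and has to be inferred.

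**1. Reproducing the plan's figure.** Evaluable patients: 105 − 16 = 89. The Hanley–McNeil variance for an AUC of A, with n₁ SND cases and n₀ others, is

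Var(A) = [A(1−A) + (n₁−1)(Q₁−A²) + (n₀−1)(Q₂−A²)] / (n₁n₀), with Q₁ = A/(2−A) and Q₂ = 2A²/(1+A).

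The sample is large enough when 0.86 − A₀ ≥ 1.96·SE(A₀) + 0.84·SE(0.86). For A₀ = 0.5, n₁ = 5 and n₀ = 84, the standard errors are 0.134 and 0.107. The right side is 1.96 × 0.134 + 0.84 × 0.107 ≈ 0.352, below the required 0.36.

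| Comparison AUC | SND cases needed | Patients needed (ratio 94:6 to 100:6) |
|---|---|---|
| 0.50 | 5 | 84 to 89 |
| 0.55 | 7 | 117 to 124 |
| 0.60 | 10 | 167 to 177 |
| 0.70 | 25 | 417 to 442 |

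Only 0.5 fits. The match to 89 needs a ratio of 100:6 between patients without and with SND. A 6% rate strictly means 94:6, which gives 5 + 79 = 84, or 100 with the drop-out allowance. The plan's figure lies on the generous side of that difference.

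**2. Is the stated power met?** With 5 SND cases among 89 patients, power against 0.5 is 82%; with 6 among 89 it is 89%. The number of cases is itself random. Averaged over a binomial count at 6%, power is about 78% with 89 patients and 84% with 105. The chance of four or fewer cases is 38% and 24% respectively.

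**3. Sensitivity at one threshold.** Expected cases: 0.06 × 89 = 5.3 and 0.06 × 105 = 6.3. Exact (Clopper–Pearson) 95% intervals:

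| Detected | Interval | Width (points) |
|---|---|---|
| 3 of 5 | 14.7% to 94.7% | 80 |
| 4 of 5 | 28.4% to 99.5% | 71 |
| 5 of 5 | 47.8% to 100% | 52 |
| 3 of 6 | 11.8% to 88.2% | 76 |
| 5 of 6 | 35.9% to 99.6% | 64 |
| 6 of 6 | 54.1% to 100% | 46 |

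The 46-point end arises only if all six cases, or none, are detected. Near the cited 90%, the width is 64 to 71 points.

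**4. Specificity.** With 84 patients without SND and 76 correctly classified (about the cited 91%), the exact interval is 82.1% to 95.8%, 14 points wide.

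**5. What more precision would cost.** Take an average exact half-width of 20 or 15 points, divide the cases by 0.06, and multiply by 105/89 for drop-out.

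| Assumed sensitivity | Half-width | SND cases | Evaluable | Enrolled |
|---|---|---|---|---|
| 90% (the figure cited in the background) | 20 | 12 | 200 | 236 |
| 90% | 15 | 19 | 317 | 374 |
| 75% (assumption) | 20 | 20 | 334 | 394 |
| 75% | 15 | 35 | 584 | 689 |

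That is 2.2 to 6.6 times the planned 105 patients, in a study planned for one year.

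**The case for a change.** The strongest case for a change is that no later document can create more SND cases. The sample size and the assumed rate are fixed in the protocol, so any list of thresholds, or any full ROC curve, inherits the same handful of cases. This is correct. A higher rate helps only partly: 9 cases (10% of 89) would give widths of 34 to 65 points, and 13 (15%) would give 25 to 56. The rate could also be lower than assumed, because the 6% covers the whole first week while Measurements counts SND only after 48 hours. Two or three sentences naming the comparison AUC and calling threshold results descriptive would cost no patients.

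The imprecision stands; the alleged mismatch does not. The sentence in the background is a single line with no list of cut-offs and no estimand. Analysing PI across all cut-offs instead of one is ROC analysis, and the AUC is its summary. On that reading, Sample Size Calculation sizes the study on the matching quantity. To say that accuracy as a whole cannot be supported also goes too far, since specificity is reasonably well estimated. The suggested sentences concern reporting (case counts, exact intervals, a descriptive label), which an SAP commonly carries. They would alter neither the sample, the data nor any result.

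**Conclusion.** No change to the plan is called for. The arithmetic of the concern is right: with 5 to 6 expected SND cases, sensitivity at one PI threshold is known only to within an interval 46 to 80 points wide. But this is limited precision for a quantity for which the protocol sets no target, not a contradiction or a missed figure. The protocol promises no precision for sensitivity, no ranking of thresholds and no recommended cut-off. Its single stated target, 80% power on the AUC, is roughly met: 82% with five cases among 89 patients, and on average 78% (89 patients) to 84% (105).

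The only remedy that would alter the results is a larger study, about 236 to 689 enrolled depending on the sensitivity and half-width assumed. Nothing in the stated aim requires it.

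The conclusion rests on a comparison AUC of 0.5, which is inferred because no higher value tried fits 89 patients; on the protocol's own 6% and 0.86; and on reading the background sentence as ROC analysis. If the authors meant to put forward a PI cut-off for use from this study alone, the widths above would weigh against it. The text does not say so. Those interpreting the results should treat threshold-level sensitivity as descriptive.

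### Does measuring everyone immediately on admission clash with recording tracings only in settled patients, and does that bias the prediction of deterioration?

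*Protocol*

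**What the plan says.** The Method paragraph describes how the middle cerebral arteries are insonated. It says "tracings will be recorded for at least 10 cardiac cycles in patients showing stable conditions" and explains stable as "no agitation or pain, no cardiorespiratory distress". A little further on it adds "Tracings will be stable over a 30-s recording period". The section then closes with "All patients will have TCD measurements immediately on admission", after which patients are classified by PI value and outcome. Under Measurements, PI "will be measured on admission then every 12hr following admission for 1st 48 hour after that every day till 7th day".

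The inclusion criterion takes adults aged 25 to 60 "presented with mild to moderate TBI (GCS 9 – 15) admitted to Emergency Hospitals within 12 hours following the trauma". It does not require the patient to be calm or free of pain. The related exclusions are "Systolic arterial blood pressure less than 90 mmHg and /or arterial pulse oximetry less than 90" (per cent), ventilation with sedation on admission, and a craniotemporal lesion that prevents a satisfactory examination. None of them covers agitation or pain.

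The protocol gives no time window for the admission reading and no rule for an enrolled patient who is not yet settled when the scan is due.

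**The concern.** Taken literally, the two statements cannot both hold for an eligible patient who is agitated or in pain on arrival. One requires a reading at once; the other withholds the recording until the patient is stable. The admission PI of that patient is then late, missing, or taken outside the stated conditions.

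Admission PI is the predictor on which the study rests. If its availability depends on clinical state, the patients with a valid reading may differ from those without one, and the AUC would describe a selected group. A reading taken after deterioration had begun would not be a prediction at all. The plan expects only about six events, so even one or two selective losses would be felt. These are fair reasons to look closely.

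**Working it through.** **1. Reproduce the planned size.** Inputs from Sample Size Calculation: AUC 0.86, deterioration in 6%, 80% power, a 5% level, 16 cases added for drop-out, total 105. Assumed because not stated: null AUC 0.5, two-sided test.

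Hanley–McNeil variance, with n1 events and n0 non-events:

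V(A) = [A(1−A) + (n1−1)(a−A²) + (n0−1)(b−A²)] / (n1·n0), where a = A/(2−A) and b = 2A²/(1+A).

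At A = 0.86, a = 0.754 and b = 0.795. Let s0 and s1 be the square roots of V(0.5) and V(0.86). The requirement is 1.96·s0 + 0.842·s1 ≤ 0.86 − 0.50 = 0.36.

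- With 5 events and 84 non-events, s0 = 0.1336 and s1 = 0.1069. The left side is 0.352, so the condition is met.
- With 4 events and 84 non-events the left side is 0.392, so it is not met.

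Five events at a non-event to event ratio of 100:6 give 5 + 84 = 89, and 89 + 16 = 105, the stated total. The strict ratio 94:6 would give 84 + 16 = 100, so the stated figure appears to rest on the former.

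**2. Power if events lose their index test.** Power = Φ[(0.36 − 1.96·s0)/s1].

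| Starting point | Events | Non-events | Power |
|---|---|---|---|
| 89 evaluable (all 16 spares used) | 5 | 84 | 82% |
| same, one event fewer | 4 | 85 | 72% |
| same, two fewer | 3 | 86 | 57% |
| 105 enrolled, 6% events | 6.3 | 98.7 | 91% |
| same, one event lost | 5.3 | 98.7 | 85% |
| same, two lost | 4.3 | 98.7 | 76% |

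The first three rows are correct arithmetic, but they charge the loss after the whole drop-out allowance has been spent. An unobtainable tracing is one of the things that allowance is there to absorb. From the enrolled number, the first lost event costs 6 points and leaves power above the planned 80%; the second costs 9 more and takes it below.

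**3. Illustrative loss rates (not in the protocol).**

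- 15.2% missing in both groups (16/105): 5.3 events, 85%.
- 30% of events and 10% of non-events missing: 4.4 events, 77%.
- 50% and 10%: 3.2 events, 60%.

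Material damage needs a large and strongly selective loss. Nothing in the protocol points to one, and nothing rules it out.

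**4. Order of test and outcome.** The Measurements list records secondary neurological deterioration after 48 hours up to day 7. The admission PI would have to slip past 48 hours, and so past the 12-hourly readings scheduled until then, before it could follow a counted event.

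**5. What immediately can mean.** Eligibility requires an initial CT, because the severe TCDB grades are excluded, and consent is obtained from each participant. An interval before the study scan is therefore built in. A strict conflict remains only for a patient who is still unsettled when that interval ends.

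**The case for a change.** The best case for a change is that this is protocol conduct, not analysis: a scan time or a reason for failure that is never written down cannot be recovered later. Reading the stability clause as a recording-quality condition does not remove the tension either, since immediacy then fails for unsettled patients. Spare recruitment replaces numbers but does not undo selective loss. In addition, the outcome definition counts sedation for neurological worsening as an event, so an agitated patient sedated before the scan could blur predictor and outcome.

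Part of this stands. The deferral rule is unwritten, and a large selective loss would matter with so few events. The 48-hour argument also has a limit: the Primary outcome line speaks only of deterioration at day 7, and if events in the first 48 hours were counted, a late reading could follow an early event.

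The rest is weaker. No sentence removes an unsettled patient from the cohort or makes that patient a drop-out, and the repeated PI schedule means that never obtaining a reading would take repeated failure. The blood pressure, oximetry and ventilation exclusions already take out part of the cardiorespiratory distress group. The remedies that come to mind are to take the first acceptable tracing as baseline, check that it precedes the event, count late and missing readings, and run a sensitivity analysis. Most of these are ordinary analytic practice or belong in an analysis plan that is not at hand.

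**Conclusion.** No change is needed. The two sentences are loosely worded together, but they have a natural joint reading: scan on admission, as soon as an acceptable tracing can be recorded. On the stated outcome window a deferral of hours does not turn the PI into a reading taken after the event. Power, which is about 91% from 105 enrolled, stays at about 85% after one lost event and drops below target, to 76%, only after two.

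These figures assume a null AUC of 0.5, a two-sided 5% test, the planned AUC of 0.86 and a 6% event rate. The point about timing assumes that the 48-hour to day 7 window defines the counted events. The share of patients affected, and any link with deterioration, cannot be derived from the protocol, so neither the size nor the direction of a bias can be claimed. What is left is missing detail of the kind that competent staff and analysts settle without an amendment.

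### The definition of secondary neurological deterioration (SND) starts counting at 48 h, while the 6% rate behind the sample size covers the whole first week

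*Protocol*

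**What the plan says.** The timing of SND appears in three places in the Protocol.

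- **Measurements.** This is the only definition. It gives two criteria in brackets (a fall in GCS, or a deterioration that warrants intervention) and closes with "osmotherapy, or neurosurgical intervention) after 48hr till the 7th day".
- **Primary outcome.** "SND at 7th day post traumatic".
- **Sample Size Calculation.** "6% of patients developed SND within the first week after trauma", together with "area under the curve (AUC) for PI to predict the outcome (SND) was 0.86", "5% confidence limit" and "80% power of the study". The total is 105, of which 16 are an allowance for dropout.

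The Method section sets the time of the index test and the use of the endpoint: "All patients will have TCD measurements immediately on admission and will be classified into groups according to PI value and the outcome". Admission may be up to 12 hours after trauma (Inclusion criteria). The stated aim is early prediction of deterioration.

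**The concern.** The definition and the planning rate describe different windows. One opens at 48 h; the other opens at trauma. The protocol does not say which governs, or whether the 48 h runs from trauma or from admission.

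Two things are at stake.

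- **Classification.** Patients are grouped by PI and by outcome. Someone who deteriorates at, say, 20 h is an SND case on the first-week wording and a non-case on the literal definition. If that patient had a high admission PI, a correct early prediction would be scored as a false positive. The events lost would be those closest to the index test, which are central to a study of early prediction.
- **Event count.** The 6% includes deteriorations in the first 48 h. If these are not counted, fewer events are available than were planned for, and the planned number is already small.

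All data are to be recorded by a physician outside the research, who has only the written definition to follow. Early events that are not recorded as SND may not be recoverable later.

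**Working it through.** **1. The three wordings side by side**

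| Place | Start | End | Origin stated? |
|---|---|---|---|
| Measurements | 48 h | day 7 | no |
| Primary outcome | not stated | day 7 | trauma |
| Sample size | trauma | end of week 1 | trauma |

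The second and third rows agree if the Primary outcome means SND at any time up to day 7. The first row cannot agree with the third when read literally. So one phrase conflicts with the other two.

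The 48 h phrase stands after the bracket that holds both criteria. It therefore applies to SND as a whole and cannot be read as a limit on the second criterion alone.

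The neighbouring entries in the same list do cover the early period. Vital signs are recorded "every 12 hr in first 48 hr then every day till 7th day", and PI follows the same pattern. The SND entry names only the later part.

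**2. Expected events**

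Evaluable patients: 105 − 16 = 89. First-week SND at 6%: 89 × 0.06 = 5.34.

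The share of SND before 48 h is not in the document. With an assumed share f, the expected counted events are 5.34 × (1 − f):

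- f = 0: 5.3
- f = 10%: 4.8
- f = 25%: 4.0
- f = 50%: 2.7

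**3. The plan's own sample size**

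The null AUC and the sidedness are not stated. With null 0.50, two-sided 5%, AUC 0.86, 80% power, a 94:6 ratio and Hanley-McNeil variances, the requirement is 5 SND + 79 non-SND = 84, or 100 with the 16 added, against the stated 89 and 105. The stated figure is not reproduced exactly. The gap is in the safe direction and does not bear on this point.

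**4. Power by number of counted events (illustration)**

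Power = Φ[(0.86 − 0.50 − 1.96 × SE0) / SE1]. SE0 and SE1 are the Hanley-McNeil standard errors at AUC 0.50 and 0.86, with k events and 89 − k non-events.

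| k | SE0 | SE1 | (0.36 − 1.96 × SE0)/SE1 | Power |
|---|---|---|---|---|
| 5 | 0.1336 | 0.1069 | 0.92 | 82% |
| 4 | 0.1485 | 0.1193 | 0.58 | 72% |
| 3 | 0.1705 | 0.1376 | 0.19 | 57% |

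This holds AUC at 0.86 for the late events and counts early SND as non-events. Both are assumptions.

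**5. Sensitivity to the null AUC**

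With 5 events, power is 82% at null 0.50, 65% at 0.55 and 46% at 0.60. The level depends heavily on a value that the protocol does not state. The dependable part of the table is the direction: each event lost to the 48 h start costs power.

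**The case against.** The strongest reply is that the 48 h phrase is a clumsy recording schedule and not an exclusion. It sits in a list whose entries often end with timing, such as "every 12 hr in first 48 hr then every day till 7th day". The labelled Primary outcome and the sample size both fit a whole-week endpoint, and nothing says that early SND is to be discarded. If the cumulative first-week reading governs, the window costs nothing. This is a fair reading and it limits how certain the harm is. It does not remove the conflict: the SND entry names only the later period, and it is the only definition a data recorder has.

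Three stronger inferences are tempting, and the document supports none of them.

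- **Three mutually incompatible windows.** Two of the three wordings agree on a cumulative reading.
- **A demonstrated loss of power.** The early share and the null AUC are both missing, so no loss of a given size can be shown.
- **A study below 80% power even with no early SND.** At AUC 0.86 and null 0.50, averaging over a random event count gives 77.8% at 89 evaluable. The usual calculation at the expected 5.3 events gives about 85%. The result turns on the method and the assumed AUC.

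The objection also stands on a related matter: the poor precision that comes with about five events is mostly a consequence of a low event rate, whatever the window.

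**Conclusion.** The point holds as a conflict between one phrase and the rest of the protocol. The only SND definition, read literally, starts at 48 h; the 6% rate covers the first week. On the literal reading, patients who deteriorate in the first 48 h after the admission Doppler are classed as non-SND, and the planned 5.3 events are an overestimate of those counted.

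How large the effect would be cannot be determined from the document. The figures of 82%, 72% and 57% power for 5, 4 and 3 events rest on an assumed null AUC of 0.50, AUC 0.86, a two-sided 5% level and 89 evaluable patients. They show only how much one or two reclassified patients can matter. Because the phrase defines the primary endpoint and decides which events are recorded, it should be settled before data collection.

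**What to change.** Use one window and one time origin in Measurements, Primary outcome and Sample Size Calculation: first occurrence of either SND criterion at any time from the admission Doppler through day 7 after trauma, as a cumulative yes/no endpoint. This is consistent with the first-week basis of the 6%. SND should then be recorded from admission.

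If the 48 h start is deliberate, the protocol should say so, state whether it runs from trauma or admission, restrict that analysis to patients free of SND at 48 h, and restate the event rate and power for that window.

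The cost is a short change of wording plus recording SND over the first 48 h. Vital signs and PI are already scheduled 12-hourly then. GCS has no stated repeat times, so its recording for the first criterion would have to be added.
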